9. MEASUREMENT OF EFFECT

9.1 Pathologic evaluation

Assessment of immune related pathologic response (irPRC) is the first secondary endpoint of the study as defined by Stein et al.⁵¹

Diagnostic pathology specimen will be collected and processed following the treating institution's standard operating procedures and will be evaluated by a head and neck pathologist.

Major pathologic response (mPR) will also be assessed and is defined as $\leq 10\%$ residual tumor

tissue on all reviewed specimens of each subject.

9.2 Radiographic evaluation

Radiographic response is the third secondary endpoint of the study. On this study, planned radiologic evaluations will be performed at baseline and after 4 weeks of therapy prior to planned surgical resection.

Response and progression will be evaluated in this study using the new international criteria proposed by the revised Response Evaluation Criteria in Solid Tumors (RECIST) guideline (version 1.1) [Eur J Ca 45:228-247, 2009], Changes in the longest diameter (unidimensional measurement) of the tumor lesions and the shortest diameter in the case of malignant lymph nodes are used in the RECIST criteria.

Evidence of PD will be based on a comparison with baseline (or nadir) scans, in which there is either an increase of 20% or more in the sum of the longest diameters (SLD) of target lesions taking as reference the smallest sum of the longest diameters (nadir) recorded since starting nivolumab treatment, and/or unequivocal progression of non-target lesions, with or without the development of 1 or more new lesions. Because all subjects are intended to get surgical resection, confirmatory scans are not required.

9.2.1 Definitions

Evaluable for toxicity. All patients will be evaluable for toxicity from the time of their first treatment on protocol.

Evaluable for objective response. All patients will be evaluable for objective response after completing the first treatment on protocol, as long as they get radiographic evaluation with either CT scans or MRI scans on the specified timeframe.

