| Creatinine OR creatinine clearance | within normal institutional limits OR $\geq 40 \text{ mL/min}$ (using modified Cockcroft-Gault formula) for patients with creatinine levels above institutional normal. |

- 3.1.9 The effects of nivolumab on the developing human fetus are unknown.
 - 1) Women of childbearing potential (WOCBP) must have a negative urine or

serum pregnancy test (minimum sensitivity 25 IU/L or equivalent units of HCG) within 24 hours prior to the start of study treatment.

- 2) Women must not be breastfeeding
- 3) Women of childbearing potential (WOCBP) must agree to follow instructions for method(s) of contraception for the duration of treatment with study treatment and for 5 months post-treatment completion. Women should use an adequate method(s) of contraception (Refer to nivolumab IB for WOCBP and methods of contraception to be provided).
- 4) Males who are sexually active with WOCBP must agree to follow instructions for method(s) of contraception for the duration of treatment with study treatment(s) and 7 months post-treatment completion. In addition, male participants must be willing to refrain from sperm donation during this time. Men who are sexually active with WOCBP must agree to follow instructions for method(s) of contraception.

3.1.10 Patient understands the study regimen,

its requirements, risks and discomforts and is able and willing to sign the informed consent form. Voluntary signed and dated IRB/IEC approved written informed consent form in accordance with regulatory and institutional guidelines must be obtained before the performance of any protocol related procedures that are not part of normal patient care. Subjects must be competent to report AEs, understand the drug dosing schedule and use of medications to control AEs.

3.1.11 Measurable disease – either radiologically (per RECIST V 1.1) or clinically measurable on exam in order to assess treatment response.

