4.1.1 Treatment overview (Cohorts 1 & 2)

After being consented, patients will undergo baseline evaluations including clinical exam, complete blood count, blood chemistry, and thyroid function test. Baseline core or surgical biopsy and images with either CT scan or MRI scan will be obtained at screening. Blood collection for correlative analyses will be performed anytime after consent and prior to Nivolumab administration. Nivolumab 480mg will be administered intravenously on approximately Day -28 prior to planned surgery on Day 0 to Day +14 (14 day window as needed for scheduling surgery/logistics). An earlier surgery date is permissible if clinically indicated – see section 4.1.2 (salvage treatment).

Patients will undergo post-treatment images and specimen collection ideally within 7 days from planned surgery date, or as clinically indicated.

Post-operative adjuvant treatment with radiotherapy or chemoradiotherapy can be delivered, if clinically indicated at the discretion of treating physician following the standard of care. All subjects will

Johns Hopkins Protocol #: J1923

get follow up imaging about 3 months after completion of curative therapy (e.g. after adjuvant therapy) as per clinical routine.

After the initial post-treatment images, further imaging will be obtained as clinically indicated. In case of recurrence, a biopsy will be obtained and the specimen will be secured for future analyses if clinically feasible.

To explore oral and gut microbial correlates of response to neoadjuvant nivolumab, stool samples and oral rinses will be collected at baseline prior to infusion and then again prior to surgery. Subjects will also be asked to fill out a medical, antibiotic use and dietary questionnaire that will be used to assess whether antibiotic use or dietary patterns correlate with features of the oral and gut microbiome.

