4.1.2 Early salvage treatment options: salvage surgery, salvage chemotherapy

In patients with clinically worsening disease, or concern that resectability may be at risk, or due to extenuating scheduling circumstances, an earlier surgery date can be approved in consultation with the treating surgeon, medical oncologist, and study team.

Alternatively, neoadjuvant chemotherapy can be given in patients with clinically worsening disease, or concern that resectability may be at risk after approval and review by the treating surgeon, and medical oncologist, and study team.

Such 'salvage' patients will continue on study, unless deemed non-evaluable for other reasons.

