4.2.4 Diagnostic and surgical evaluations

All patients enrolled on this protocol must be surgical candidates with either locally recurrent SCCHN or oligometastatic SCCHN. Patients will have undergone radiographic evaluation indicating no evidence of disease outside the planned surgical field and main/target lesion/s should be determined to be amenable for resection by the treating surgeon.

Distant metastatic disease is permissible if a clinical indication for surgery exists (e.g. in order to provide symptom control) and such distant disease can be addressed at an interval with systemic therapy (e.g. chemotherapy, targeted therapies, etc), or local therapies (e.g. radiation, metastatectomy) as clinically indicated.

Any further preoperative testing that is recommended by the surgeon or anesthesiologist will be performed as part of standard of care. Surgery for patients enrolled on this protocol will be according to generally accepted standards of care. Patients should have baseline imaging as clinically appropriate of the affected area (neck/chest/abdomen and/or pelvis) – e.g. a CT or MRI with IV contrast and appropriate imaging should be repeated after completing neoadjuvant therapy, within the 7 days prior to planned surgery to assess response.

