- c. Patients are to be provided with a stool collection kit during screening (days -42 to -29) and instructed to collect a stool sample within 48 hours of their scheduled infusion day (day -28).
- d. Oral rinse is considered an optional collection during the first and second year follow up visits.

*CT abdomen/pelvis can be added if there's a clinical indication. MRI may replace or supplement CT scans if clinically appropriate.

Ideally same imaging modality should be used for sequential imaging assessments.

** can be done on day of surgery also if necessary.

† MRI can be used at the treating physician's discretion; ideally same modality should be used throughout.

(X) as clinically indicated

*** Blood for correlates may be collected anytime after consent and prior to Nivolumab infusion.

Johns Hopkins Protocol #: J1923

***** Days -42 until/including Day -28

\$\$ F/u visits are allowable +/- 28 days or as clinically indicated

[See Appendix D](#) for Sociodemographic Characteristics Questionnaire

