10.1.2 Endpoints

Primary Endpoint

Safety and feasibility of neoadjuvant nivolumab administration in patients with newly diagnosed head and neck cancer and those with locoregional recurrence or oligometastatic disease undergoing surgical resection, measured by 1) frequency of drug-related adverse events occurring up to 100 days after the last dose of nivolumab or 30 days after surgery (whichever is longer), and 2) successful completion of preoperative treatment and proceeding to surgery without any extended treatment-related delays greater than 28 days from the preplanned day 0 (or 14 days from day +14).

Secondary Endpoints

Immune related pathologic response (irPRC)
As defined by Stein et al (CCR 2019)⁵¹

Major pathologic response rate

Defined as $\leq 10\%$ residual tumor in the resection specimen after neoadjuvant nivolumab

Progression-free survival

Progression-free survival will be measured from the time of initiation of nivolumab until radiologic or clinical progression or death.

Radiographic response rate

Response will be determined by RECIST version 1.1.

Laboratory correlates of immune activity and response

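### Radiographic response is evaluable only in patients scanned on schedule, so treated patients who worsen and go early to surgery or chemotherapy may leave the denominator and raise the rate

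*Combined protocol and SAP*

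**What the plan says.** All references are to the combined protocol and SAP.

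- **Endpoint.** Radiographic response rate is a secondary endpoint (1.2 and 10.1.2): "Response will be determined by RECIST version 1.1".
- **Evaluability.** Under 9.2.1, patients are evaluable for objective response after the first treatment "as long as they get radiographic evaluation with either CT scans or MRI scans on the specified timeframe".
- **Analysis.** Section 10.3 describes pathologic complete response, progression-free survival and toxicity. For radiographic response it gives no denominator, no rule for a missing or off-window scan, and no confidence interval. By contrast, 10.2 defines the safety and feasibility populations as patients who receive one dose.
- **Early departure from the schedule.** Section 4.1.2 permits earlier surgery for worsening disease, threatened resectability or scheduling reasons. It permits neoadjuvant chemotherapy for the first two. It does not ask for a scan beforehand. Such "patients will continue on study, unless deemed non-evaluable for other reasons".
- **Timing of the post-dose scan.** Section 9.2 says "planned radiologic evaluations will be performed at baseline and after 4 weeks of therapy prior to planned surgical resection". Section 4.2.4 says "within the 7 days prior to planned surgery to assess response". Section 4.1.1 says "ideally within 7 days from planned surgery date, or as clinically indicated". The calendar in 4.10 places the pre-surgical evaluation on Days −7 to −1, with a footnote that it "can be done on day of surgery also if necessary".
- **Measurable disease.** Criterion 3.1.11 requires it of everyone: "either radiologically (per RECIST V 1.1) or clinically measurable on exam in order to assess treatment response".

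**The concern.** A response rate is easiest to interpret when its denominator is fixed at the start of treatment. Here, membership depends on something that happens afterwards, namely a scan obtained in a window just before surgery. Clinical worsening is one of the stated reasons for leaving the planned schedule, and a patient who leaves it may miss that scan. Such a patient is unlikely to be a responder. If the patient is dropped rather than counted as a non-response, the numerator is unchanged, the denominator shrinks and the rate rises.

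A second consequence concerns salvage chemotherapy. These patients stay on study, and nothing says that the response assessment must precede the chemotherapy. A later pre-surgical scan could credit shrinkage after chemotherapy to nivolumab.

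At stake is the credibility of a secondary activity estimate in a small trial. The primary safety and feasibility analyses are not affected.

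**Working it through.** **Plan figures.** The documents give no expected rate, target or precision for radiographic response, so there is no figure for this endpoint to reproduce. As a check on method, the exact (Clopper-Pearson) intervals tabulated in 10.2 for n = 12 were recomputed. All five match, including 2/12 = 16.7% with 2.1% to 48.4%.

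**Inputs.** N = 12 (expected per cohort) and N = 26 (maximum total) come from 10.2. The number of responders r and the number without an in-window scan m are not in the documents. The values below are assumptions.

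**Formula.** If the unscanned patients are all non-responders:

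- all-treated rate = r/N
- scanned-only rate = r/(N−m)
- ratio = N/(N−m)

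| N | r | m | All treated | Scanned only | Difference (points) | Ratio |
|---|---|---|---|---|---|---|
| 12 | 2 | 1 | 16.7% | 2/11 = 18.2% | 1.5 | 1.09 |
| 12 | 2 | 2 | 16.7% | 2/10 = 20.0% | 3.3 | 1.20 |
| 12 | 2 | 3 | 16.7% | 2/9 = 22.2% | 5.6 | 1.33 |
| 26 | 5 | 2 | 19.2% | 5/24 = 20.8% | 1.6 | 1.08 |
| 26 | 5 | 4 | 19.2% | 5/22 = 22.7% | 3.5 | 1.18 |
| 26 | 5 | 6 | 19.2% | 5/20 = 25.0% | 5.8 | 1.30 |
| 26 | 8 | 2 | 30.8% | 8/24 = 33.3% | 2.6 | 1.08 |
| 26 | 8 | 6 | 30.8% | 8/20 = 40.0% | 9.2 | 1.30 |

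**Against the sampling error.** The exact 95% interval at 5/26 is 6.6% to 39.4%, a width of 32.8 points. At 2/12 it is 46.3 points wide. The interval moves to 8.7% to 49.1% at 5/20, and to 2.8% to 60.0% at 2/9. Every shift in the table is well inside the all-treated interval.

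**When unscanned patients can respond.** Let p be the response rate in scanned patients and q the rate in unscanned patients. Then bias = p − [(N−m)p + mq]/N = (m/N)(p − q). Take p = 18%, an assumed value borrowed from the rate that 2.2.2 quotes for another anti-PD-1 agent, with N = 26 and m = 4:

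- q = 0: all-treated rate = (22 × 0.18)/26 = 15.2%, bias +2.8 points
- q = 18%: bias 0
- q = 36%: all-treated rate = (22 × 0.18 + 4 × 0.36)/26 = 20.8%, bias −2.8 points

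The bias is upward only where the unscanned respond less often than the scanned. That is the natural expectation for patients who left the schedule because they were worsening. It is not for those moved for scheduling reasons.

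**Which timeframe applies.** With dosing on Day −28, the calendar window of Days −7 to −1 falls 21 to 27 days after the dose. Read strictly, the four-week statement in 9.2 is not met in that window even by a patient exactly on schedule, and a patient operated on before Day 0 cannot meet it at all. Under 4.1.1, 4.2.4 and the 4.10 footnote, which tie the scan to surgery or clinical need, an early-surgery patient scanned shortly beforehand could be in window. The same patient is evaluable or not depending on which section is applied.

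**The case against.** The strongest reply is that the loss of worsening patients is possible but not shown. Most of the timing text follows the surgery date, and 4.1.1 also allows a scan on clinical indication, which could cover a patient who is getting worse. Early surgery can be for scheduling alone, and salvage patients stay on study. All of this stands, and it is why the bias is a risk and not a certainty.

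It can also be said that 9.2.1 defines evaluability while 10.3 names no denominator, so the denominator is inferred. That is correct. But 9.2.1 is the only definition of an analysis set for this endpoint, and nothing elsewhere overrides it.

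The endpoint carries no hypothesis, threshold or decision rule, and progression-free survival separately captures clinical progression. Comparing radiographic with pathologic response, a stated secondary objective, needs patients with both a scan and a specimen, so a new denominator for the rate would not alter that comparison. These points limit the importance of the matter but leave the rule as it is.

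A reader might go further and infer that patients with only clinically measurable disease are excluded, and that this too pushes the rate up. The documents do not support that. Section 9.2.1 asks for a CT or MRI to be done, not for a lesion measurable on it. The calendar schedules CT for every patient at screening and before surgery, and 9.2.2 and 9.2.3 accept caliper measurement. Even if such patients were lost, the sign of the bias would depend on their own response rate, for which the documents give no value.

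**Conclusion.** The concern holds in a limited form. As written, evaluability depends on a post-treatment scan in a window that the document states in several ways. Clinical worsening is a recognised route out of that schedule, and no text turns an unassessed patient into a non-response. The rate may therefore be biased upward, by a factor N/(N−m) if all unscanned patients are non-responders. In the illustrations this is 1.5 to 5.6 points for one cohort of 12 with 2 responders and 1 to 3 unscanned, and 1.6 to 5.8 points for 26 patients with 5 responders and 2 to 6 unscanned. The responder and missing-scan counts are assumptions.

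The shifts are small beside the sampling error of a descriptive endpoint, so this does not threaten the trial's main conclusions. It is still worth correcting before data are seen, because the choice among the timing statements could otherwise be made after results are known. It would be too strong to say that worsening patients will drop out or that the rate is certain to be inflated.

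**What to change.** In 9.2.1 and 10.3:

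1. Define the denominator for the radiographic response rate as all patients who received nivolumab, including any later replaced for accrual. This matches the safety and feasibility populations, and 3.1.11 already requires measurable disease, so no further restriction is needed.
2. Count a patient with no post-dose response assessment before surgery or salvage therapy as a non-responder.
3. Report the scanned-only rate as a sensitivity analysis. Give exact 95% intervals for both rates, and the number unscanned by reason (worsening or scheduling).
4. Reconcile the scan-timing statements in 4.1.1, 4.2.4, 4.10 and 9.2 into one definition for the analysis, so that an early-surgery patient who was scanned beforehand is not excluded.

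This is a wording change that needs no new procedures or patients. The reported rate may be slightly lower. Patients moved early for scheduling who were never scanned would also count as non-responders, which is conservative for them. The tabulation by reason and the sensitivity analysis let a reader see how much this matters.

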9.2.2 Disease Parameters

To assess objective response or future progression, it is necessary to estimate the overall tumor burden at baseline and use this as a comparator for subsequent measurements. Measurable disease is defined by the presence of at least one measurable lesion.

Measurable disease. Measurable lesions are defined as those that can be accurately measured in at least one dimension (longest diameter to be recorded) as >20 mm by chest x-ray or as >10 mm with CT scan, MRI, or calipers by clinical exam. All tumor measurements must be recorded in millimeters (or decimal fractions of centimeters).

Note: Tumor lesions that are situated in a previously irradiated area are not considered measurable unless there has been demonstrated progression in the lesion.

Malignant lymph nodes. To be considered pathologically enlarged and measurable, a lymph node must be >15 mm in short axis when assessed by CT scan (CT scan slice thickness recommended to be no greater than 5 mm). At baseline and in follow-up, only the short axis will be measured and followed.

Non-measurable disease. All other lesions (or sites of disease), including small lesions (longest diameter <10 mm or pathological lymph nodes with ≥ 10 to <15 mm short axis), are considered non-measurable disease. Bone lesions, leptomeningeal disease, ascites, pleural/pericardial effusions, lymphangitic involvement of the skin or lung, inflammatory breast disease, and abdominal masses/abdominal organomegaly (not followed by CT or MRI), are considered as non-measurable.

Note: Cystic lesions that meet the criteria for radiographically defined simple cysts should not be considered as malignant lesions (neither measurable nor non-measurable) since they are, by definition, simple cysts.

'Cystic lesions' thought to represent cystic metastases can be considered as measurable lesions, if they meet the definition of measurability described above. However, if non-cystic lesions are present in the same patient, these are preferred for selection as target lesions.

Target lesions. All measurable lesions up to a maximum of 2 lesions per organ and 5 lesions in total, representative of all involved organs, should be identified as **target lesions** and recorded and measured at baseline. Target lesions should be selected on the basis of their size (lesions with the longest diameter), be representative of all involved organs, but in addition should be those that lend themselves to reproducible repeated measurements. It may be the case that, on occasion, the largest lesion does not lend itself to reproducible measurement in which circumstance the next largest lesion which can be measured reproducibly should be selected. A sum of the diameters (longest for non-nodal lesions, short axis for nodal lesions) for all target lesions will be calculated and reported as the baseline sum diameters. If lymph nodes are to be included in the sum, then only the short axis is added into the sum. The baseline sum diameters will be used as reference to further characterize any objective tumor regression in the measurable dimension of the disease.

Non-target lesions. All other lesions (or sites of disease) including any measurable lesions over and above the 5 target lesions should be identified as non-target lesions and should also be recorded at baseline. Measurements of these lesions are not required, but the presence, absence, or in rare cases unequivocal progression of each should be noted throughout follow-up.

9.2.3 Methods for Evaluation of Measurable Disease

All measurements should be taken and recorded in metric notation using a ruler or calipers. All baseline evaluations should be performed as closely as possible to the beginning of treatment and never more than 4 weeks before the beginning of the treatment.

The same method of assessment and the same technique should be used to characterize each identified and reported lesion at baseline and during follow-up. Imaging-based evaluation is preferred to evaluation by clinical examination unless the lesion(s) being followed cannot be imaged but are assessable by clinical exam.

Clinical lesions Clinical lesions will only be considered measurable when they are superficial (e.g., skin nodules and palpable lymph nodes) and ≥ 10 mm diameter as assessed using calipers (e.g., skin nodules). In the case of skin lesions, documentation by color photography, including a ruler to estimate the size of the lesion, is recommended.

Conventional CT and MRI This guideline has defined measurability of lesions on CT scan based on the assumption that CT slice thickness is 5 mm or less. If CT scans have slice thickness greater than 5 mm, the minimum size for a measurable lesion should be twice the slice thickness. MRI is also acceptable in certain situations (e.g. for body scans).

Use of MRI remains a complex issue. MRI has excellent contrast, spatial, and temporal resolution; however, there are many image acquisition variables involved in MRI, which greatly impact image quality, lesion conspicuity, and measurement. Furthermore, the availability of MRI is variable globally. As with CT, if an MRI is performed, the technical specifications of the scanning sequences used should be optimized for the evaluation of the type and site of disease. Furthermore, as with CT, the modality used at follow-up should be the same as was used at baseline and the lesions should be measured/assessed on the same pulse sequence. It is beyond the scope of the RECIST guidelines to prescribe specific MRI pulse sequence parameters for all scanners, body parts, and diseases. Ideally, the same type of scanner should be used and the image acquisition protocol should be followed as closely as possible to prior scans. Body scans should be performed with breath-hold scanning techniques, if possible.

PET-CT At present, the low dose or attenuation correction CT portion of a combined PET-CT is not always of optimal diagnostic CT quality for use with RECIST measurements. However, if the site can document that the CT performed as part of a PET-CT is of identical diagnostic quality to a diagnostic CT (with IV and oral contrast), then the CT portion of the PET-CT can be used for RECIST measurements and can be used interchangeably with conventional CT in accurately measuring cancer lesions over time. Note, however, that the PET portion of the CT introduces additional data which may bias an investigator if it is not routinely or serially performed.

Ultrasound Ultrasound is not useful in assessment of lesion size and should not be used as a method of measurement. Ultrasound examinations cannot be reproduced in their entirety for independent review at a later date and, because they are operator dependent, it cannot be guaranteed that the same technique and measurements will be taken from one assessment to the next. If new lesions are identified by ultrasound in the course of the study, confirmation by CT or MRI is advised. If there is concern about radiation exposure at CT, MRI may be used instead of CT in selected instances.

